5.6 Blood Products

During the administration of selinexor and ibrutinib, patients may receive red blood cell (RBC) or platelet transfusions, if clinically indicated, per institutional guidelines. These transfusions should be leukopore filtered and irradiated. Patients who require repeated transfusion support should be discussed with the principal investigator.

Patients may receive supportive care with G-CSF or GM-CSF in accordance with institutional guidelines prior to entry and throughout the study.

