Grade 3 without bleeding	
Rule out other causes including drug effects.
 
For first occurrence: skip 1 dose and reduce selinexor by 1 dose level.
 
If recurrent, unless contraindicated, start treatment with moderate to high doses of thrombopoietin stimulating agents such as romiplostim 5 to 10 µg/kg SC weekly (preferred) or eltrombopag 100 to 150 mg QD.
 
In cases where there is significant disease involvement in the bone marrow or pre-existing compromised marrow function (eg, due to prior marrow-toxic therapy), or if there is baseline thrombocytopenia Grade 2-4 at baseline, the Investigator in consultation with the Medical Monitor may decide to continue selinexor dosing without dose reductions and/or interruptions as specified above, provided that platelet counts and bleeding symptoms/signs are closely monitored. Thrombopoietin stimulating agents are recommended.

Grade 4 without bleeding	
Rule out other causes including drug effects.
 
Interrupt selinexor until patient recovers to Grade 2 or baseline. Selinexor dosing may be reduced by 1 dose level (it is recommended to have only 1 dose modification per cycle).
 
If recurrent, unless contraindicated, start treatment with moderate to high doses of thrombopoietin stimulating agents as above.
 
In cases where there is significant disease involvement in the bone marrow or pre-existing compromised marrow function (eg, due to prior marrow-toxic therapy), the Investigator in consultation with the Medical Monitor may decide to continue selinexor dosing without dose reductions and/or interruptions as specified above, provided that platelet counts and bleeding symptoms/signs are closely monitored.

Grade ≥ 3 with bleeding	
Interrupt selinexor dosing and check platelet counts weekly until the bleeding has stopped, patient is clinically stable and the platelets have recovered to Grade 2 or baseline. When resuming selinexor, reduce by 1 dose level.
 
If recurrent, unless contraindicated, start treatment with moderate to high doses of thrombopoietin stimulating agents as above.

Neutropenia	

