11.1.3 Response Criteria for CLL Patients

Definition of Response for CLL Patients: Criteria for response will utilize the IWCLL Response criteria¹⁴.

Complete response (CR):

CR requires all of the following criteria as assessed at least 2 months after completion of therapy:

- Peripheral blood lymphocytes (evaluated by blood and differential count) below $4 \times 10^9/L$ ($4000/\mu L$). The presence of minimal residual disease (MRD) after therapy should be assessed. The sensitivity of the method used to evaluate for MRD should be reported.
- Absence of significant lymphadenopathy (e.g., lymph nodes > 1.5 cm in diameter) by CT scan of the abdomen, pelvis, and thorax.
- No hepatomegaly or splenomegaly by physical examination.
- Absence of constitutional symptoms.
- Blood counts above the following values:
 - Neutrophils more than $1.5 \times 10^9/L$ ($1500/\mu L$) without need for exogenous growth factors.
 - Platelets more than $100 \times 10^9/L$ ($100\,000/\mu L$).
 - Hemoglobin more than 110 g/L (11.0 g/dL) without red blood cell transfusion or need for exogenous erythropoietin.
- A marrow aspirate and biopsy should be performed at least 2 months after the last treatment and if clinical and laboratory results as above demonstrate that a CR has been achieved.
 - To define a CR, the marrow sample must normocellular for age, with less than 30% of nucleated cells being lymphocytes. Lymphoid nodules should be absent. If lymphoid nodules are present then these nodules should be recorded as nodular PR. However, immunohistochemistry should be performed to define whether these nodules are composed primarily of T cells or lymphocytes other than CLL cells or of CLL cells. If the marrow is hypocellular, a repeat determination should be performed after 4 weeks, or until peripheral blood counts have recovered. However, this time interval should not exceed 6 months after the last treatment. A marrow biopsy should be compared with that of pretreatment marrow. The quality of the CR should be assessed for MRD by flow cytometry or by immunohistochemistry (IHC).

CR with incomplete marrow recovery (CRi):

All the criteria for a CR (including the marrow examination) have been met though there is persistent anemia or thrombocytopenia or neutropenia apparently unrelated to CLL but related to drug toxicity.

Partial response (PR) PR is defined as follows:

- A decrease in the number of blood lymphocytes by 50% or more from the value before therapy.

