- Reduction in lymph node size by 50% or more either in the sum products of up to 6 lymph nodes, or in the largest diameter of the enlarged lymph node(s) detected prior to therapy.
- No increase in any lymph node, and no new enlarged lymph node. In small lymph nodes (< 2 cm), an increase of less than 25% is not considered to be significant.
- A reduction in the noted pretreatment enlargement of the spleen or liver by 50% or more, as detected by CT scan.
- The blood count should show one of the following results:
- Neutrophils more than $1.5 \times 10^9/L$ ($1500/\mu L$) without need for exogenous growth factors.
- Platelet counts greater than $100 \times 10^9/L$ ($100\,000/\mu L$) or 50% improvement over baseline.
- Hemoglobin greater than 110 g/L (11.0 g/dL) or 50% improvement over baseline without requiring red blood cell transfusions or exogenous erythropoietin.

Progressive Disease:

Characterized by at least one of the following:

- Appearance of any new lesion, such as enlarged lymph nodes (>1.5 cm), splenomegaly, hepatomegaly, or other organ infiltrates.
- An increase by 50% or more in greatest determined diameter of any previous site.
- An increase in the previously noted enlargement of the liver or spleen by 50% or more or the de novo appearance of hepatomegaly or splenomegaly.
- An increase in the number of blood lymphocytes by 50% or more with at least 5000 B-lymphocytes per microliter.
- Transformation to a more aggressive histology (e.g., Richter syndrome). Whenever possible, this diagnosis should be established by lymph node biopsy.
- Occurrence of cytopenia (neutropenia, anemia, or thrombocytopenia) attributable to CLL. During therapy, cytopenias cannot be used to define disease progression.
- The progression of any cytopenia (unrelated to autoimmune cytopenia), as documented by a decrease of Hb levels by more than 20 g/L (2 g/dL) or to less than 100 g/L (10 g/dL), or by a decrease of platelet counts by more than 50% or to less than $100 \times 10^9/L$ ($100\,000/\mu L$), which occurs at least 3 months after treatment, defines disease progression, if the marrow biopsy demonstrates an infiltrate of clonal CLL cells.

Stable Disease:

Patients who do not fulfill the criteria for complete or partial response as defined above but do not exhibit progressive disease will be considered as having stable disease.

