13.2 Sample Size/Accrual Rate

For cohort 1 and 2, with groups of 2-3 patients per month enrolled in the dose finding study, it is expected that approximately 9 groups of patients will be treated over 18-30 months. Expansion at the MTD is expected to accrue over 6-12 months. Thus, the total study duration is estimated to be 24-42 months. On average, we expect 32 patients to be enrolled, but the total sample size could be as many as 50 patients and will depend on the dose escalation and composition of CLL and NHL patients treated at the estimated MTD as part of the dose-finding portion of the study.

Cohort 3 will be a pilot study to gain data on the ability of selinexor to deepen responses with ibrutinib. Ten patients who have been treated with ibrutinib as their frontline therapy for CLL/SLL for at least 12 cycles and have obtained PR will be accrued to this cohort, and selinexor will be added to ibrutinib for 14 more cycles. The deepening of response rate is defined as the percentage of patients who convert to a MRD negative complete response (MRD- CR) from PR at the end of 14 cycles of selinexor plus ibrutinib among this cohort. If we observe 3 or more patients out of 10 who achieve the conversion from PR to MRD-CR, we will consider this regimen promising and move it forward for further study. For various true deepening of response rates, the table below shows the probability of observing at least 3 MRD-CRs in 10 patients. For example, if the true deepening response rate is 30%, then the probability of declaring the regimen promising is 61.7% with 10 patients.

True Deepening of Response Rate	Probability of Observing 3 or More MRD-CR in 10 Patients
0.1	0.070
0.2	0.322
0.25	0.474
0.3	0.617
0.35	0.738
0.4	0.833

With an accrual rate of 2 patients per month, we expect accrual to be complete in 5 months.

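### The CLL response criteria require unsupported neutrophil and hemoglobin counts but not unsupported platelets, so a support-dependent CRi can be scored as CR and may count toward Cohort 3's 3-of-10 rule

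*Combined protocol and SAP*

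**What the plan says.** **Response criteria (11.1.3, CLL).** The CR hemoglobin line reads "Hemoglobin more than 110 g/L (11.0 g/dL) without red blood cell transfusion or need for exogenous erythropoietin". The CR neutrophil line likewise excludes exogenous growth factors. The platelet line between them begins "Platelets more than", gives the 100 × 10⁹/L threshold and stops there. The PR list repeats the pattern. Neutrophils and hemoglobin are qualified, while the platelet line reads "Platelet counts greater than $100 \times 10^9/L$ ($100\,000/\mu L$) or 50% improvement over baseline" with no condition on support. For PR, one of the three count lines is enough.

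**CRi (11.1.3).** This separate category is for patients who meet all CR criteria but have "persistent anemia or thrombocytopenia or neutropenia apparently unrelated to CLL but related to drug toxicity".

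**Platelet support.** Three rows of the thrombocytopenia guidance in 5.18 (Grade 3 without bleeding, Grade 4 without bleeding, Grade 3 or higher with bleeding) bring in thrombopoietin agents when the event recurs, unless contraindicated. The later rows say to "start treatment with moderate to high doses of thrombopoietin stimulating agents as above". No stopping point for the agent is given. Section 5.6 says that on treatment "patients may receive red blood cell (RBC) or platelet transfusions, if clinically indicated, per institutional guidelines".

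**Cohort 3 rule (13.2).** "If we observe 3 or more patients out of 10 who achieve the conversion from PR to MRD-CR", the regimen is called promising and moves forward. Sections 13.2 and 13.5.4 place the endpoint at the end of 14 cycles. Sections 13.2, 13.5.4 and 13.8.2 do not mention CRi.

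**The concern.** For two of the three cell lines, the protocol treats a supported count as no evidence of marrow recovery. For the third it is silent, although its own guidance directs or permits support for that line during treatment. The gap therefore blurs the boundary between CR and CRi. A patient already on a thrombopoietin agent, or recently transfused, whose platelets pass the threshold only for that reason satisfies the CR list.

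The label matters most in Cohort 3. Its only go-forward rule counts MRD-negative CRs in ten patients, so a single reclassified patient can decide the outcome. Section 5.19 also ties its Cohort 3 discontinuation wording to MRD-negative CR and does not place CRi.

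In the relapsed CLL patients, the CR category is affected in the same way, but no decision rule rests on it.

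**Working it through.** **1. Is the gap closed elsewhere?** I looked for a condition on platelet support in 11.1.3, 13.2, 13.3, 13.5, 13.8 and the study calendars and found none.

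**2. Reproduce the plan's table.** The inputs are n = 10 and a threshold of 3 (13.2). The formula is P(X ≥ 3) = 1 − Σ (x = 0 to 2) C(10,x) pˣ (1−p)¹⁰⁻ˣ.

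| True rate | Plan | Exact binomial |
|---|---|---|
| 0.10 | 0.070 | 0.0702 |
| 0.20 | 0.322 | 0.3222 |
| 0.25 | 0.474 | 0.4744 |
| 0.30 | 0.617 | 0.6172 |
| 0.35 | 0.738 | 0.7384 |
| 0.40 | 0.833 | 0.8327 |

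All six entries agree, so the arithmetic of the rule is sound. The question is only who counts as a success.

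**3. Sensitivity by share of scored responses.** Let f be the share of scored MRD-negative CRs that depend on platelet support. This share is assumed; the documents give no figure. With a true rate p, the scored rate is p / (1 − f).

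| f | Scored rate, p = 0.10 | P(≥3 of 10) | Scored rate, p = 0.20 | P(≥3 of 10) |
|---|---|---|---|---|
| 0 | 0.1000 | 0.0702 | 0.2000 | 0.3222 |
| 0.05 | 0.1053 | 0.0795 | 0.2105 | 0.3542 |
| 0.10 | 0.1111 | 0.0906 | 0.2222 | 0.3899 |
| 0.20 | 0.1250 | 0.1195 | 0.2500 | 0.4744 |

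**4. Sensitivity with exactly one such patient.** Two successes among the other nine then suffice. At a true rate of 0.10 in those nine:

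- P(≥2 of 9) = 1 − 0.9⁹ − 9 × 0.1 × 0.9⁸ = 1 − 0.3874 − 0.3874 = 0.225.
- The design figure for ten patients is 0.070. If this one patient is instead a failure, three of the other nine are needed: 0.2252 − 36 × 0.01 × 0.9⁷ = 0.2252 − 0.1722 = 0.053.

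**5. How often one patient would be decisive.** Exactly two true successes in ten has probability 45 × 0.01 × 0.9⁸ = 0.194 at a true rate of 0.10, and 45 × 0.04 × 0.8⁸ = 0.302 at 0.20.

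**6. Timing.** Section 11.1.3 assesses CR at least 2 months after therapy is completed; 13.2 and 13.5.4 count it at the end of 14 cycles. Support is more likely to be in place under the second reading. The two sections have to be reconciled before the effect on the rule is settled.

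**7. Can support be identified from the data?** Section 5.4 has concomitant medications recorded throughout participation. I found no explicit requirement to record platelet transfusions. The Cohort 3 calendar appears to mark neither a blood count nor concurrent medications at Cycle 14 Day 1, although the table may have been damaged in extraction.

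**The case against.** Several counter-arguments have force.

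- **Platelet support cannot create depth of response.** MRD negativity, node resolution and marrow clearance are all still required. A support-dependent patient has deepened in that sense, and deepening is the aim in objective 1.2.4. This stands. It is why the sponsor should decide whether CRi counts. If it does count, the 3-of-10 result is unaffected by the gap.
- **An assessor could already choose CRi**, because its definition covers persistent drug-related thrombocytopenia. That is possible, but the CR list as written is also met, so two assessors could differ.
- **The 2-month delay in 11.1.3 may remove the problem.** It would reduce it, but the Cohort 3 sections set a different time.
- **11.1.3 adopts published IWCLL criteria**, which cannot be checked here. The judgment rests on the criteria as the protocol writes them out.
- **The PR gap is minor.** Platelets decide PR only when neutrophils and hemoglobin both fail. Cohort 3's entry PR precedes selinexor, so only the descriptive response rate is affected.

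A reader might also infer more than the text supports:

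- *That the chance of passing rises to 0.18 or 0.32.* Those values follow from adding 5 or 10 points to a true 10%. They imply that a third (5/15) or half (10/20) of scored MRD-negative CRs depend on support, and nothing in the documents suggests such shares.
- *That any patient with moderately low platelets, say 60,000/µL, would be lifted into CR.* Section 5.18 brings in agents for recurrent Grade 3, Grade 4 or bleeding events, and 5.6 requires a clinical indication for transfusion. The route is a patient already on an agent or recently transfused.
- *That 5.18 recommends agents for everyone with low baseline platelets.* That sentence sits in the row for on-study Grade 3 events and concerns patients whose dosing is continued without modification.

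**Conclusion.** The inconsistency is real. The CLL platelet lines lack the no-support condition that the neutrophil and hemoglobin lines carry, and nothing else in the documents supplies it. As written, a support-dependent drug-related thrombocytopenia can be scored CR instead of CRi.

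An effect on the Cohort 3 rule is conditional. It requires that CRi does not count as MRD-negative CR, and that the end-of-cycle-14 time governs rather than the 2-month delay. Under those assumptions and a true rate of 10%, the chance of declaring the regimen promising moves from 0.070 to about 0.08–0.12 for assumed shares of 5–20%, and to 0.225 if exactly one of the ten patients is of this kind. These are sensitivity values, not estimates. The documents do not show that the rule will in fact be inflated.

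This is a consistency correction worth making because it is nearly free and the rule can turn on one patient.

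**What to change.** 1. In 11.1.3, add *without platelet transfusion or thrombopoietin-stimulating agent* to the CR platelet line. Add it to the PR platelet line too, for consistency; that change touches only the descriptive response rate.
2. In 13.2 and 13.5.4, state whether CRi counts as MRD-negative CR. Either answer is workable if fixed in advance.
3. Reconcile the CR assessment time in 11.1.3 with the end-of-cycle-14 endpoint.
4. Ensure that the blood count, concomitant medications and any platelet transfusion are recorded at that assessment.

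The cost is a few phrases and a small addition to data collection. The probability table in 13.2 is unchanged, and so is patient management. CR and MRD-negative CR rates may come out slightly lower.

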5.19 Duration of Therapy

In the absence of treatment delays due to adverse event(s), treatment may continue indefinitely or until one of the following criteria applies:

- Disease progression,
- Intercurrent illness that prevents further administration of treatment,
- Unacceptable adverse event(s),
- Patient decides to withdraw from the study, or
- General or specific changes in the patient's condition render the patient unacceptable for further treatment in the judgment of the investigator.
- Patients enrolled in Cohort 3 will discontinue therapy in a response-adapted manner. All patients will discontinue selinexor after 14 cycles. Patients who achieve a MRD negative CR at 14 cycles will discontinue both selinexor and ibrutinib. Patients who achieve a MRD – PR will discontinue both selinexor and ibrutinib at discretion of treating physician. Patients with any other response are recommended to continue ibrutinib indefinitely.

5.20 Duration of Follow Up

Patients will be followed every 6 months until progression or an alternative therapy is started. Patients removed from study for unacceptable adverse event(s) will be followed until resolution or stabilization of the adverse event. Follow-up data will be required unless consent is withdrawn.

5.21 Criteria for Removal from Treatment

At the discretion of the Investigator, the investigator may remove a patient from the study treatment for the following reasons:

- Death,
- Disease progression,
- Noncompliance with study procedures,
- Intercurrent illness that prevents further administration of treatment,
- Need of treatment with medications not allowed by the study protocol,
- Unacceptable adverse event(s),
- Other treatments become available,
- Treatment delays exceeding 28 days,
- Patient decides to withdraw from the study, or
- General or specific changes in the patient's condition render the patient unacceptable for further treatment in the judgment of the investigator.

The reason for study removal and the date the patient was removed must be documented in the Case Report Form. Patients who are removed from protocol therapy will still be followed for progression and survival.

6. DOSING DELAYS/DOSE MODIFICATIONS

Toxicities that occur in cycle 1 that are DLTs (Section 4.2) will result in protocol removal. Adverse events that are not defined as DLTs and / or occur in cycles 2 and higher will lead to dose delays and modifications as detailed below. No dose reduction below ibrutinib 140 mg and selinexor 20 mg/week will be allowed. If a patient experiences several adverse events, and there are conflicting recommendations, the investigator should use the recommended dose adjustment that reduces the dose to the lowest level. Missed doses will not be replaced. Treatment delays for adverse events exceeding 28 days will lead to protocol removal unless approved by the principal investigator.

Ibrutinib-related lymphocytosis, for the purposes of this protocol, is defined as an elevation in blood lymphocyte count of $\geq 50\%$ compared with baseline count in conjunction with unequivocal improvement in at least 1 other disease-related parameter including lymph node size, spleen size,

hematologic parameters (hemoglobin or platelets), or disease-related symptoms. Ibrutinib-associated treatment-related lymphocytosis generally occurs within the first few weeks of therapy, peaks within the first few months, and resolves slowly. Patients with isolated lymphocytosis in the setting of reduced disease burden or improvement in hemoglobin/platelets should not be considered to have progressive disease.

Asymptomatic treatment-related lymphocytosis should not be considered an adverse event. Subjects with treatment-related lymphocytosis in the absence of other disease-related symptoms should be encouraged to remain on study treatment and continue with all study-related procedures.

6.1 Dose adjustment guidelines for hematologic ibrutinib or selinexor-related toxicities

Toxicities that are clearly not related to ibrutinib or selinexor will not require a dosing modification. Similarly, toxicities that are clearly attributable to an individual drug will only require modification of that drug, with modifications following the tables below.

Event Name	Neutropenia, Anemia, or Thrombocytopenia For Patients with Baseline Absolute Neutrophil Count $\geq 1000/\text{mm}^3$; Hemoglobin $\geq 11\text{g/dL}$; or Platelets $\geq 100,000/\text{mm}^3$	
Grade of Event	Management/Next Dose Ibrutinib*	Management/Next Dose of Selinexor*
< Grade 3	No change in dose	No change in dose
\geq Grade 3	Hold until neutrophils, hemoglobin, or platelets have returned to < Grade 3. • 1 st occurrence: No change in dose • 2 nd occurrence: Cohort 1 and 3 = No change in dose; Cohort 2 = Decrease ibrutinib to next lowest dose level • 3 rd occurrence: Decrease ibrutinib to next lowest dose level • 4 th occurrence: Patient comes off study	Hold until neutrophils, hemoglobin, or platelets have returned to < Grade 3. • 1 st occurrence: No change in dose • 2 nd occurrence: Decrease selinexor to next lowest dose. • 3 rd occurrence: No change in dose • 4 th occurrence: Patient comes off study
*Dose reductions < ibrutinib 140mg daily or selinexor 20 mg weekly are not permitted. Recommendations: - Full supportive care, growth factors, and transfusions should be given as medically indicated. - If the patient tolerates a reduced dose for two cycles, patient may be dose escalated to the dose they received prior to the reduction after authorization from Principal Investigator.		

Event Name	Neutropenia, Anemia, or Thrombocytopenia For Patients with Baseline Absolute Neutrophil Count $\leq 1000/\text{mm}^3$; Hemoglobin $\leq 11\text{g/dL}$; or Platelets $\leq 100,000/\text{mm}^3$
------------	---

Grade of AE	Management/Next Dose Ibrutinib*	Management/Next Dose of Selinexor*
<Grade 3	No change in dose	No change in dose
≥ Grade 3	
Hold until neutrophils, hemoglobin, or platelets have returned to within 50% of pretreatment values. If initial value is within 50% of pretreatment value, no hold is needed.
 
 • 1st occurrence: No change in dose • 2nd occurrence: Cohort 1 and 3= No change in dose; Cohort 2 = Decrease ibrutinib to the next lowest dose level. • 3rd occurrence: Decrease ibrutinib to the next lowest dose level. • 4th occurrence: Patient comes off study 	
Hold until neutrophils, hemoglobin, or platelets have returned to within 50% of pretreatment values. If initial value is within 50% of pretreatment value, no hold is needed.
 
 • 1st occurrence: No change in dose. Initiate granulocyte colony-stimulating factors for grade >3 neutropenia. • 2nd occurrence: Decrease selinexor to next lowest dose. • 3rd occurrence: No change in dose • 4th occurrence: Decrease selinexor to the next lowest dose • 5th occurrence: No change in dose • 6th occurrence: Discontinue selinexor

*Dose reductions < ibrutinib 140mg daily or selinexor 20 mg weekly are not permitted.
 
Recommendations:
 
 -Full supportive care, growth factors, and transfusions should be given as medically indicated. - If the patient tolerates a reduced dose for two cycles, patient may be dose escalated to the dose they received prior to the reduction after authorization from Principal Investigator. 		

Event Name	Bleeding	
Grade of Event	Management/Next Dose Ibrutinib*	Management/Next Dose of Selinexor*
≤ Grade 2 (mild to moderate)	
Hold ibrutinib for at least 7 days after last bleeding and until platelets return to ≥ 50% of baseline value.
 
 • 1st occurrence: Restart ibrutinib at next lowest dose level. In cases where no bleeding is observed after 6 days of dosing return to full dose at the physician's discretion. • 2nd occurrence: Restart ibrutinib at next lowest dose level. • 3rd occurrence: Patient comes off study. 	
Hold selinexor for at least 7 days after last bleeding and until platelets return to ≥ 50% of baseline value.
 
 • 1st occurrence: Restart selinexor at next lowest dose level. In cases where no bleeding is observed after 6 days of dosing return to full dose at the physician's discretion. • 2nd occurrence: Restart selinexor at next lowest dose level. • 3rd occurrence: Patient comes off study.

≥ Grade 3 (severe)	Hold ibrutinib for at least 7 days after last bleeding and until platelets return to ≥ 50% of baseline value. 
 • 1st occurrence: Restart ibrutinib at next lowest dose level. • 2nd occurrence: Patient comes off study. 	Hold selinexor for at least 7 days after last bleeding and until platelets return to ≥ 50% of baseline value. 
 • 1st occurrence: Restart selinexor at next lowest dose level. • 2nd occurrence: Patient comes off study.
*Dose reductions < ibrutinib 140mg daily or selinexor 20 mg weekly are not permitted. Recommendations: -Full supportive care, growth factors, and transfusions should be given as medically indicated.		

Event Name	Neutropenic Fever	
Grade of Event	Management/Next Dose Ibrutinib*	Management/Next Dose of Selinexor*
Grade 3	Hold until toxicity ≤ Grade 2 or baseline. 
 • 1st occurrence: No change in dose. • 2nd occurrence: Decrease ibrutinib to next lowest dose level. • 3rd occurrence: Patient comes off study. 	Hold until toxicity ≤ Grade 2 or baseline. 
 • 1st occurrence: Decrease selinexor to next lowest dose. • 2nd occurrence: No change in dose. • 3rd occurrence: Patient comes off study.
Grade 4	Hold until toxicity ≤ Grade 2 or baseline. 
 • 1st occurrence: Decrease ibrutinib to next lowest dose level. • 2nd occurrence: Decrease ibrutinib to next lowest dose level. • 3rd occurrence: Patient comes off study 	Hold until toxicity ≤ Grade 2 or baseline. 
 • 1st occurrence: Decrease selinexor to next lowest dose. • 2nd occurrence: Decrease selinexor to next lowest dose level. • 3rd occurrence: Patient comes off study
*Dose reductions < ibrutinib 140mg daily or selinexor 20 mg weekly are not permitted. Recommendations: -Full supportive care and/or growth factors should be given as medically indicated.		

